Statistical Methods and Data Analysis:	
Phase 1:
 
Designed to determine the RP2D and toxicity profile of ibrutinib using the modified 3+3+3 design. Up to 3 dose levels will be explored. In observing ≤ 2 DLTs in 9 subjects, RP2D is determined.
 
The Phase 1b efficacy data for subjects with RP2D will be combined with Phase 2 efficacy data.
 
Phase 2
 
Primary Efficacy Analysis:
 
Best overall cGVHD response rate is defined as the proportion of subjects who achieve a NIH-defined complete response (CR) or partial response (PR) during the study over all subjects who got RP2D from either Phase 1b portion or Phase 2 portion. The cGVHD response rate along with its 95% exact binomial confidence interval will be presented.
 
Secondary Efficacy Analyses:
 
Secondary efficacy variables including sustained response rate, DOR,

	
corticosteroid requirement changes over time, and change in symptom burden as measured by the Lee cGVHD Symptom Scale will be analyzed descriptively.
 
Efficacy analyses will be performed on all subjects who are enrolled for RP2D from either Phase 1b portion or Phase 2 portion.
 
Safety Analysis:
 
All subjects are to be monitored for adverse events during the study. Other safety measurements include clinical laboratory tests and vital signs. Descriptive statistics will be use to summarize safety data (adverse events [AEs], clinical laboratory tests and vital signs) for all subjects receiving ibrutinib. Summary statistics will include means, standard deviations, and medians for continuous variables and proportions for categorical variables.

Interim Analysis	Not applicable.

ABBREVIATIONS

AE	adverse event
aGVHD	acute GVHD
Allo-HCT	allogenic hematopoietic cell transplant
ALT	alanine aminotransferase
ANC	absolute neutrophil count
ASBMT	American Society for Blood and Marrow Transplantation
ASCO	American Society of Clinical Oncology
AST	aspartate aminotransferase
AUC	area under the curve
BAFF	B cell activating factor
BCR	B-cell receptor
BSA	body surface area
Btk	Bruton's tyrosine kinase
CFR	US Code of Federal Regulations
cGVHD	chronic GVHD
CLL	chronic lymphocytic leukemia
CNS	central nervous system
CRF	case report form
CR	complete response
CTCAE v. 4.03	Common Terminology Criteria for Adverse Events version 4.03
CYP	cytochrome P450
DLT	dose limiting toxicity
DOR	Duration of response
ECG	Electrocardiogram
ECP	extracorporeal photopheresis

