 11. Moderate or severe hepatic impairment (Child-Pugh classification, see [Appendix K](#)).
 12. Subject has a concurrent illness which in the opinion of the investigator may interfere with the treatment and evaluation of the patient.
 13. Concomitant use of warfarin or other Vitamin K antagonists
 14. Subject has a known allergy or hypersensitivity to ibrutinib.
 15. Vaccinated with live, attenuated vaccines within 4 weeks of first dose of ibrutinib.
 16. Known bleeding disorders (eg, von Willebrand's disease or hemophilia).
 17. History of stroke or intracranial hemorrhage within 6 months prior to enrollment.
 18. Known history of human immunodeficiency virus (HIV) or active with hepatitis C virus (HCV) or hepatitis B virus (HBV). Subjects who are positive for hepatitis B core antibody, hepatitis B surface antigen, or hepatitis C antibody must have a negative polymerase chain reaction (PCR) result before enrollment. Those who are PCR positive will be excluded.
 19. Major surgery within 4 weeks of first dose of ibrutinib.
 20. Concurrent use of a strong cytochrome P450 (CYP) 3A inhibitor ([Appendix I](#)).
 21. Unable to swallow capsules or malabsorption syndrome, disease significantly affecting gastrointestinal function, or resection of the stomach or small bowel, symptomatic inflammatory bowel disease or ulcerative colitis, or partial or complete bowel obstruction.
 22. Unable to understand the purpose and risks of the study and to provide a signed and dated informed consent form (ICF) and authorization to use protected health information (in accordance with national and local subject privacy regulations).

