5.3.1.4. Dose Modification for Adverse Reactions

During Phase 1b, ibrutinib will be stopped according to DLT rules in [Section 5.2.1](#) during the 28 day DLT window. Thereafter, subjects enrolled in Phase 1b will have ibrutinib modified or discontinued according to the guidelines in [Table 1](#).

For Phase 2, the dose of ibrutinib should be modified according to the dose modification guidelines in [Table 1](#) if any of the following toxicities occur:

- Grade 3 ANC (<1,000/ μ L) with an associated temperature $\geq 38.5^{\circ}\text{C}$
- Grade 4 ANC (<500/ μ L) for more than 7 days. Refer to [Section 6.1.1](#) for instruction regarding the use of growth factor support
- Grade 3 thrombocytopenia (<50,000/ μ L) in the presence of Grade ≥ 2 bleeding events
- Grade 4 thrombocytopenia (<25,000/ μ L)

- Grade 3 or 4 nausea, vomiting, or diarrhea if persistent, despite optimal anti-emetic and/or anti-diarrheal therapy
- Any other Grade 4 or unmanageable Grade 3 toxicity attributed to ibrutinib

Table 1: Ibrutinib Dose Modifications

Hematologic Adverse Events	
Occurrence	Action to be Taken
First	Withhold ibrutinib until recovery to an ANC ≥ 750 or platelets $> 25,000$ with no evidence of Grade ≥ 2 bleeding; may restart at original dose level
Second	Withhold ibrutinib until recovery to an ANC ≥ 750 or platelets $> 25,000$ with no evidence of Grade ≥ 2 bleeding; may restart at 1 dose level lower
Third	Withhold ibrutinib until recovery to an ANC ≥ 750 or platelets $> 25,000$ with no evidence of Grade ≥ 2 bleeding; may restart at 1 dose level lower
Fourth	Discontinue ibrutinib ^a
Non-Hematologic Adverse Events	
First	Withhold ibrutinib until recovery to Grade ≤ 1 or baseline; may restart at original dose level
Second	Withhold ibrutinib until recovery to Grade ≤ 1 or baseline; may restart at 1 dose level lower
Third	Withhold ibrutinib until recovery to Grade ≤ 1 or baseline; may restart at 1 dose level lower
Fourth	Discontinue ibrutinib ^a

^a. If ibrutinib is discontinued for toxicity, subject will end the Treatment Phase of the study.

For Grade 3 or 4 atrial fibrillation or persistent atrial fibrillation of any grade, consider the risks and benefits of ibrutinib treatment. If clinically indicated, the use of anticoagulants or antiplatelet agents may be considered for the thromboprophylaxis of atrial fibrillation ([Section 6.2.4](#)).

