6.2. Medications to be Used with Caution

6.2.1. CYP3A Inhibitors/Inducers

Ibrutinib is metabolized primarily by CYP3A. Avoid co-administration with strong CYP3A (eg, ketoconazole, indinavir, nelfinavir, ritonavir, saquinavir, clarithromycin, telithromycin, itraconazole, and nefazadone) or moderate CYP3A inhibitors and consider alternative agents with less CYP3A inhibition. If a strong CYP3A inhibitor must be used, reduce ibrutinib dose to 140 mg or withhold treatment temporarily for the duration of the inhibitor use. Subjects should be monitored for signs of ibrutinib toxicity. If a moderate CYP3A inhibitor must be used, reduce ibrutinib to 140 mg for the duration of the inhibitor use. No dose adjustment is required in combination with mild inhibitors. Avoid grapefruit and Seville oranges during ibrutinib treatment, as these contain moderate inhibitors of CYP3A (see [Section 5.3.1.2](#)).

Avoid concomitant use of strong CYP3A inducers (eg, carbamazepine, rifampin, phenytoin, and St. John's Wort). Consider alternative agents with less CYP3A induction.

A list of common CYP3A inhibitors or inducers is provided in [Appendix J](#); a comprehensive list of inhibitors, inducers, and substrates may be found at <http://medicine.iupui.edu/clinpharm/ddis/table.aspx>. This website is continually revised and should be checked frequently for updates.

For the most comprehensive effect of CYP3A inhibitors or inducers on ibrutinib exposure, please refer to the current version of the IB.

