10.1. Subject Information

The following definitions will be used for the safety and efficacy analysis, respectively:

- **Safety population:** All enrolled subjects who receive at least one dose of study drug.
- **Efficacy population:** All enrolled subjects who receive at least one RP2D of study drug.

Additional analysis populations, which might be used for sensitivity analyses and biomarker studies, are defined in the SAP.

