4.7 Extent of Study drug Exposure

The exposure to study drugs will be summarized. The following parameters will be summarized when applicable:

- Duration of treatment
- Cumulative dose received on study
- Dose intensity
- Relative dose intensity
- Dose reduction due to AE
- Dose interruption with 7 days or more due to AE

5. Efficacy Analysis

Unless specified otherwise, all information from the Phase 1b and Phase 2 parts of the study will be combined for efficacy analysis. The primary population used to evaluate efficacy is All Treated Population and where applicable, the response evaluable analysis set will be used as a sensitivity analysis to assess the robustness of the results.

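### The protocol defines its efficacy set by receipt of an RP2D dose in one place and by enrollment to the RP2D in another; under the receipt rule, membership can depend on post-baseline events

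*Protocol*

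**What the plan says.** Protocol 10.1 sets the efficacy population by what was taken: "All enrolled subjects who receive at least one RP2D of study drug". The synopsis (Statistical Methods and Data Analysis) has two wordings. The denominator of the primary endpoint is receipt-based, "over all subjects who got RP2D from either Phase 1b portion or Phase 2 portion". A later sentence is enrollment-based: "Efficacy analyses will be performed on all subjects who are enrolled for RP2D from either Phase 1b portion or Phase 2 portion".

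The opening paragraph of SAP Section 5 states a third rule: "The primary population used to evaluate efficacy is All Treated Population". It adds that "all information from the Phase 1b and Phase 2 parts of the study will be combined for efficacy analysis", with no restriction to the RP2D in that sentence.

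Four other provisions decide who can be affected:

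- **Eligibility.** Exclusion criterion 20 (Protocol 4.2) bars only the strong class: "Concurrent use of a strong cytochrome P450 (CYP) 3A inhibitor". A subject on a moderate inhibitor can enroll.
- **Interaction rule.** Protocol 6.2.1 advises avoiding moderate inhibitors, then says: "If a moderate CYP3A inhibitor must be used, reduce ibrutinib to 140 mg for the duration of the inhibitor use".
- **Dose levels.** Protocol 5.2.1 starts at 420 mg, the highest level, and moves only downward. A subject with a DLT in the 28-day window stops treatment. The synopsis (Study Design) lets the other Phase 1b subjects continue at their Phase 1 dose.
- **Later reductions.** After the window, Table 1 in Protocol 5.3.1.4 applies to Phase 1b subjects. At a second or third occurrence the subject "may restart at 1 dose level lower".

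**The concern.** In a single-arm trial the denominator of the response rate should be fixed by something known at enrollment. A rule based on receiving a particular dose lets later events decide who counts.

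There are two ways this can happen. A subject assigned to the RP2D but held at 140 mg by a co-medication is counted only if the co-medication stops while ibrutinib continues. A subject who leaves treatment early has less time for that to happen, so the rule could tend to remove early failures. In the other direction, a subject assigned to a higher level enters the RP2D set by having toxicity, recovering and restarting lower. The endpoint is best response during the study, and nothing in 10.1 or 10.2.1 limits it to responses after the first RP2D dose, so a response at the higher dose is carried in. Subjects at that higher level who were never reduced stay out.

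At stake is whether the response rate describes the subjects assigned to the RP2D, and whether two analysts reading the same protocol would use the same denominator.

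**Working it through.** **Step 1. The plan's own figure and the pass mark.** Inputs: n = 40, true rate 50%, success if the lower 95% bound exceeds 25% (Protocol 10.3), exact binomial interval (Protocol 10.4). The exact lower bound L(x, n) is the 2.5% quantile of a Beta(x, n − x + 1) distribution.

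- L(16, 40) = 24.86% and L(17, 40) = 27.04%, so 17 responders are needed.
- Power = P(X ≥ 17 | 40, 0.5) = 86.6%.
- The stated figure of at least 90% is reproduced by a normal approximation, Φ[(0.25√40 − 1.96√(0.25 × 0.75))/0.5] = Φ(1.46) = 92.9%, or by a Wilson interval (16 responders suffice), 92.3%. The gap to the exact interval is a separate matter. Only the pass mark of 17/40 is used below.

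**Step 2. Who is in the set under each rule.**

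| Subject | Receipt rule (10.1) | Enrollment rule (synopsis) |
|---|---|---|
| Assigned to an RP2D of 420 or 280 mg; moderate inhibitor from Day 1 throughout treatment | out | in |
| Same, but takes one RP2D dose later | in | in |
| Assigned to a level above the RP2D; reduced to the RP2D after the DLT window | in | out |
| Assigned to a level above the RP2D; never reduced | out | out |
| Assigned to a level above the RP2D; DLT in the window, treatment stopped | out | out |

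The rules disagree in rows 1 and 3. Row 1 differs from row 2, and row 3 from row 4, only by post-baseline events.

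**Step 3. When each route is open.**

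- RP2D 420 mg: row 1 is possible; row 3 is empty because no higher level exists.
- RP2D 280 mg: both are possible.
- RP2D 140 mg: row 1 closes on the inhibitor route, because 140 mg is then the RP2D; row 3 is possible.

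Row 3 is bounded by cohort size, at most 9 per higher level. If that level was abandoned because three subjects had DLTs, those three stopped treatment and at most 9 − 3 = 6 remain. The documents give no frequency for either row.

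**Step 4. How small a shift could matter.** These are illustrations at the threshold, not predictions.

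| Change | Before | After |
|---|---|---|
| One non-responder left out | 16/40: 24.86%, fails | 16/39: 25.57%, passes |
| Three non-responders added | 17/40: 27.04%, passes | 17/43: 24.98%, fails |
| One responder added | 16/40: 24.86%, fails | 17/41: 26.32%, passes |

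Away from the threshold, shifts of this size would not change the conclusion.

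**The case against.** The strongest reply is that the receipt basis is deliberate and mostly consistent. Protocol 3.1 continues enrollment until about 40 subjects receive the RP2D, SAP 1.4 bases power on 40 subjects receiving it, and the synopsis denominator for the primary endpoint agrees with 10.1. On this view one general synopsis sentence is the outlier, and requiring a dose at the studied level is a common treated-set rule.

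The routes are also narrow. Protocol 5.2.3 says Phase 2 subjects are treated with the RP2D, and no section expressly plans a lower start. Moderate inhibitors are to be avoided, and one started during treatment would normally follow an RP2D dose. The second route needs an RP2D below 420 mg and a reduction after the window.

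Much of this stands. In particular, a reader might infer that the set could shrink to 32 or 28 subjects, with exact power falling to 81.1% or 71.4%. The documents do not support that: a subject who never takes the RP2D does not count toward the 40, so accrual continues. Nor do they support any assumed share of subjects on moderate inhibitors; Appendix J only lists drugs.

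The reply does not remove the conflict between the two synopsis sentences. It also does not justify a rule that admits subjects from another level because of later toxicity. The RP2D was unknown when the rule was written, so the rule has to work for all three doses.

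**Conclusion.** The point holds as an inconsistency with conditional consequences. The protocol gives two rules for its efficacy set, and the one in 10.1 lets post-baseline events decide membership by two routes. The first requires an RP2D of 420 or 280 mg and a moderate inhibitor used from Day 1 throughout treatment. The second requires an RP2D below 420 mg and a later reduction to it.

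The number of subjects affected is unknown and probably small. It would change the primary conclusion only near the threshold, where one to three subjects can suffice. No loss of N or power follows.

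A reader might also infer that the trial's final primary denominator is selected in this way. That cannot be asserted: the SAP names the All Treated Population, and its definition is not in the text available for this review, so nothing is concluded from it. What can be said is that the protocol's stated rule is flawed and does not agree with the synopsis. It should be corrected.

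**What to change.** Redefine the efficacy population in Protocol 10.1 as all subjects assigned at enrollment to the RP2D level, in Phase 1b or Phase 2, who receive at least one dose of ibrutinib. State that subjects assigned to another level are excluded even if later dosed at the RP2D. Then bring four places into line: the two synopsis sentences, the accrual count in Protocol 3.1, the sample size statement in SAP 1.4, and the efficacy population in SAP Section 5.

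The cost is one sentence in 10.1 plus conforming edits. With accrual counted on the same basis, N stays at about 40 and the exact pass mark stays at 17/40. The small downside is that some included subjects will have taken less than the RP2D. No dose or clinical rule changes.

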10.2. Endpoints

10.2.1. Primary Endpoints

Phase 1b:

Safety and Tolerability

Drug toxicity will be described and graded according to [CTCAE v. 4.03](#) criteria. Dose limiting toxicities are defined in [Section 5.2.2](#). Only toxicities which occur during the first 28 days on ibrutinib will count towards the assessment of DLTs.

Toxicities which occur after the first 28 days for Phase 1b subjects will be described and graded according to [CTCAE v. 4.03](#) criteria and presented in tabulated form. This will also be performed for subjects enrolled in the Phase 2 portion of the study.

Phase 2:

The primary efficacy endpoint is the best overall cGVHD response rate. Best overall cGVHD response rate is defined the proportion of subjects who achieve a NIH-defined complete response or partial response.

Please refer to [Section 7.2.1](#) for the definition of overall cGVHD response.

10.2.2. Secondary Efficacy Endpoints

10.2.2.1. Rate of Sustained Response for at Least 5 Months

Sustained response for at least 5 months is defined as NIH-defined complete response or partial response that was sustained for at least 5 months.

10.2.2.2. Duration of Response (DOR)

Duration of response is defined as the interval between the date of initial documentation of a response, and the date of first documented evidence of progressive disease, death, or date of censoring if applicable, for responders only. Percentage of subjects with sustained response and its 95% confidence interval will be calculated using normal approximation to the binomial distribution. Subjects who stop the study drug and start new GVHD treatment before documentation of disease progression will be censored on the date of the last adequate disease assessment that is on or before the start date of new GVHD therapy. Responders are subjects who achieve a NIH-defined complete response or partial response during the study. Non-responders will be excluded from the analysis for DOR.

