10.4. Efficacy Analysis

Best overall cGVHD response rate and its 95% confidence interval will be calculated with the exact test for binomial distribution.

The secondary efficacy endpoint rate of sustained response for at least 5 months will be evaluated in the same manner as best overall cGVHD response rate.

The distribution (median and Kaplan-Meier curves) and estimates of DOR will be provided using Kaplan-Meier estimates for responders.

Other secondary endpoints, such as on corticosteroid requirement changes over time, change in symptom burden measured by the Lee cGVHD Symptom Scale will be summarized by descriptive statistics.

Exploratory endpoints will be summarized by descriptive statistics.

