5.1 Primary Endpoint

The primary efficacy endpoint is the best overall cGVHD response rate during the study based on investigator assessments. To assess the primary endpoint, the study used the 2005 NIH Consensus Panel Response criteria with two modifications based on the updated 2014 NIH Consensus Panel Response criteria: 1) “Not Evaluable” can be used for assessments where there is another non-cGVHD cause for the abnormalities documented and 2) a change in cGVHD organ score from 0 to 1 is no longer considered progression as is the case per the 2005 NIH cGVHD Response Criteria.

Best overall cGVHD response rate is defined as the proportion of subjects who achieve a NIH-defined complete response or partial response. The response rate and its 95% confidence interval (CI) will be calculated based on the exact test for binomial distribution. If the lower bound of the CI of the response rate is $\geq 25\%$, the primary efficacy objective is achieved.

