5.2 Secondary Endpoints

In order to preserve the study wise two-sided type I error rate of 0.05, rate of sustained response will be tested at the two-sided significance level of 0.05 if the primary endpoint, best overall cGVHD response rate, achieves statistical significance. Other secondary endpoints will be summarized with descriptive statistics. No formal statistical testing is planned for the other secondary endpoints.

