5.2.1 Rate of Sustained Response

Sustained response is defined as NIH-defined response that sustain continuously for at least 5 months (140 days). Considering 3 days visit window allowed by protocol, the bound of sustained response is defined as 137 days. Intermittent SD assessment between response assessments is allowed. Of the total number of subjects who responded to study treatment, the proportion of subjects who meet the sustained response criterion will be summarized in the same manner as the primary endpoint. If the lower bound of the CI of the response rate is $\geq 25\%$, this secondary objective is achieved.

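### Protocol 10.2.2.2 gives the sustained-response rate a normal-approximation interval, contradicting the exact interval in Protocol 10.4 and the SAP; the harm is to the reported limits, not to the test

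*Protocol*

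**What the plan says.** Protocol 10.2.2.1 defines sustained response of at least 5 months but names no interval method. The method appears one section later, in the paragraph on duration of response (10.2.2.2): "Percentage of subjects with sustained response and its 95% confidence interval will be calculated using normal approximation to the binomial distribution".

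Protocol 10.4 says of the same endpoint: "rate of sustained response for at least 5 months will be evaluated in the same manner as best overall cGVHD response rate". The method for that comparator is given in the same section: "Best overall cGVHD response rate and its 95% confidence interval will be calculated with the exact test for binomial distribution".

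The SAP agrees with 10.4. SAP 5.2.1 takes responders as the denominator and says "the proportion of subjects who meet the sustained response criterion will be summarized in the same manner as the primary endpoint". SAP 5.1 defines that manner: "The response rate and its 95% confidence interval (CI) will be calculated based on the exact test for binomial distribution".

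The decision rule is in the SAP only. SAP 5.2 makes sustained response the one secondary endpoint with a formal test, at two-sided 0.05 and only after the primary endpoint succeeds. SAP 5.2.1 decides it by the interval: "If the lower bound of the CI of the response rate is $\geq 25\%$, this secondary objective is achieved". The protocol synopsis describes the secondary efficacy variables, sustained response included, as analysed descriptively.

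**The concern.** A test decided by a confidence bound needs one interval method, fixed in advance. Here the protocol gives two for the same proportion. The normal approximation behaves poorly at small denominators and at rates near 100%. Both are plausible here, because the SAP's denominator is responders: about 20 if half of 40 subjects respond, and responders may well sustain at a high rate. Three things could be at stake: the pass or fail verdict on sustained response, the study-wise error rate that SAP 5.2 sets out to preserve, and the accuracy of the interval reported. These need separate checks, because the answers differ.

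**Working it through.** **Inputs.** N = 40 treated at the RP2D and a 50% response rate (Protocol 10.3, SAP 1.4). Success bound 25% for the primary endpoint (SAP 5.1) and for sustained response (SAP 5.2.1). Denominator for sustained response: responders (SAP 5.2.1). The plan states no power, assumed rate or sample size for sustained response, so there is no plan figure to reproduce. Its 90% power claim concerns the primary endpoint and does not bear on this point.

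**Formulas.** For x sustained of n responders:
- Normal (plain Wald): p ± 1.96·√(p(1−p)/n), with p = x/n.
- Exact (Clopper-Pearson): the lower limit is the 2.5% quantile of Beta(x, n−x+1); the upper limit is the 97.5% quantile of Beta(x+1, n−x), or 100% if x = n.

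**Step 1: which denominators can be tested.** The primary endpoint must pass first. At N = 40, 16 responders give an exact lower bound of 24.9% (fail) and 17 give 27.0% (pass). The tested denominator is therefore 17 to 40.

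**Step 2: pass or fail on those denominators.** The smallest x with a lower bound of at least 25% is the same under both methods at every n from 17 to 44. Examples:

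| n | exact | normal |
|---|---|---|
| 17 | 9 | 9 |
| 20 | 10 | 10 |
| 30 | 13 | 13 |
| 40 | 17 | 17 |

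If all 40 subjects were the denominator, the verdict would again not differ.

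**Step 3: where the methods do disagree.** Between n = 8 and n = 44 they disagree only at 5/8, 6/11 and 8/16.
- With 8 responders the primary gate passes only if N is 15 or less, and with 11 only if N is 24 or less. Neither is near 40.
- With 16 responders it passes only if N is 39 or less (16/39 has an exact lower bound of 25.6%).
- At 8/16 the normal lower bound is 0.5 − 1.96·√(0.25/16) = 0.5 − 0.245 = 25.5%; the exact bound is 24.7%.
- The chance of this result is P(16 respond of N) × P(8 sustain of 16). The second factor is at most 0.196. For N = 34 to 39 the first is at most 0.136. The product is at most 2.7%, whatever the true rates.

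**Step 4: error of the gated sequence.** Take a true sustained rate of 25% and let the true response rate run from 25% to 100%. The error is the sum, over responder counts r that pass the gate, of P(r responders) × P(sustained count reaches the normal-rule threshold for r). For every N from 34 to 44 it is at most 2.1%, below the one-sided 2.5%. At N = 40 it equals the error of the exact rule, because the thresholds are the same.

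**Step 5: the reported interval at n = 20.** For 19/20: √(0.95 × 0.05/20) = 0.04873, times 1.96 is 0.0955, so the normal limits are 0.95 ± 0.0955. For 20/20 the normal standard error is zero, and the exact lower limit is 0.025^(1/20) = 83.2%.

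| sustained | normal | exact |
|---|---|---|
| 15/20 | 56.0–94.0% | 50.9–91.3% |
| 18/20 | 76.9–103.1% | 68.3–98.8% |
| 19/20 | 85.4–104.6% | 75.1–99.9% |
| 20/20 | 100–100% | 83.2–100% |

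The normal upper limit exceeds 100% at 17, 18 and 19 of 20. Actual coverage of the nominal 95% interval at n = 20, summing binomial probabilities over the counts whose interval contains the true rate:

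| true rate | normal | exact |
|---|---|---|
| 80% | 92.1% | 97.8% |
| 90% | 87.6% | 98.9% |

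**The case against.** The strongest reply is that the sentence is leftover text with no effect on any decision. It sits under duration of response, and the SAP's own section on that endpoint (5.2.2) does not carry it over. Protocol section 10 calls itself a general description and leaves specifics to the SAP. The SAP, the only place with a success rule, refers to the exact method. All of that stands, and it is why the point is minor. It does not remove the contradiction: Protocol 10.4 and 10.2.2.2 still disagree within one document, and SAP 5.2.1 reaches the exact method only by cross-reference.

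A reader might go further and infer that the normal approximation can flip the verdict on the tested secondary endpoint and so breaks the study-wise error control. The documents do not support that. Considered alone, the normal rule at n = 16 has a one-sided error of 2.7% at a true rate of 25%, and at n = 11 it has 3.4%. Those figures are conditional on one responder count. A count of 11 cannot pass the gate near the planned size, and 16 cannot pass it with 40 treated. Over the gated sequence as a whole, the error stays at or below 2.1%.

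**Conclusion.** The contradiction is certain from the text, and the normal-approximation sentence is the one to remove. Its size is small. With 40 treated and the gate passed, pass or fail on sustained response is the same under both methods. The single reachable exception is 8 of exactly 16 responders, which needs 39 or fewer treated. Type I error control holds. What would suffer if the sentence were followed is the published interval: at high sustained rates among about 20 responders it runs above 100% or collapses to zero width, overstates the lower limit by about 10 points at 19/20 (85.4% against 75.1%), and covers less than its nominal 95%.

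This rests on four assumptions: responders as denominator, as in SAP 5.2.1; an exact interval for the primary gate; between 34 and 44 treated as a reading of approximately 40; and the plain normal interval, since the protocol does not say which form it means. A continuity-corrected form would be stricter than exact by one response at several denominators (18, 21, 24, 27 and 30, for example), so it could change a verdict, but only towards failure. That is a further reason not to leave the sentence in. Severity: minor.

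**What to change.** Delete the normal-approximation sentence from Protocol 10.2.2.2. State in Protocol 10.2.2.1 that the sustained-response rate is reported with an exact (Clopper-Pearson) 95% confidence interval, and name the same method in SAP 5.2.1 instead of relying on the reference to the primary endpoint. The cost is about one sentence in each document and a somewhat wider reported interval. No extra data or subjects are needed, and the result matches what Protocol 10.4 and the SAP already prescribe.
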